### 6.4. Handling of Dropouts or Missing Data

Intercurrent events (ICH E9 R1) are events which occur after the treatment initiation and make it impossible to measure a variable or influence how it would be interpreted.

Depending on the estimand being addressed, different methods will be used to handle missing data as a result of intercurrent events. Intercurrent events can occur through the following:

- application of one of the censoring rules (including after permanent study drug discontinuation or after rescue therapy)
- discontinuation

- missing an intermediate visit prior to discontinuation or rescue
- lost to follow-up.

Non-censor intercurrent events are events that are not due to the application of any censoring rule, i.e., the last 3 items in the list above.

Note that as efficacy and health outcome data can accrue after a patient permanently discontinues study drug or begins rescue therapy, specific general censoring rules to the data will be applied to all efficacy and health outcome observations subsequent to these events depending on the estimand being addressed. These specific censoring rules are described below.

The *primary censoring rule* will censor efficacy and health outcome data after permanent study drug discontinuation or after rescue therapy. This censoring rule will be applied to all continuous and categorical efficacy and health outcome endpoints. This censoring rule is equivalent to using all the data up to rescue.

A *secondary censoring rule* will only censor efficacy and health outcome data after permanent study drug discontinuation. This sensitivity analysis will include all observed values up to study drug discontinuation. The secondary censoring rule will be applied to primary and key secondary efficacy and health outcome endpoints as sensitivity analyses.

Table JAIY.6.1 describes the planned imputation methods for efficacy and health outcome endpoints with associated censoring rules. Sections 6.4.1 through 6.4.5 summarize the methodology of each imputation rule.

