For moderate potency TCS, the dispensed tube weight with cap (without the carton) in Japan is 13.5g. For countries supplied by European distributors, the dispensed weight of moderate potency TCS is 38g. The remaining countries, supplied by US distributors, the weight of moderate potency TCS is 40g. The total amount of background TCS, provided by sponsor, will be summarized in grams by potency (low and moderate) and both potencies, between visits (Week 0 through Week 1, Week 1 through Week 2, Week 2 through Week 4, Week 4 through Week 8, Week 8 through Week 12, Week 12 through Week 16), and throughout the entire 16-week treatment period. If a returned tube is not weighed or not returned, then the tube can be classified as partially used, fully used, unused, or unknown. Partially used rescue medication tubes will be defined as 50% used whereas fully used and unused tubes will be defined as 100% and 0% used respectively. When drug accountability is not performed for a particular tube of rescue medication or an answer of 'unknown' is given for a tube which is not returned, that particular tube will not be included in the analysis. The main analysis on the total amount of background TCS throughout the entire 16-week treatment period will apply censoring rule #1. After patients who get rescued or discontinue IP, whichever is earlier, it is assumed that they would use the same amount of TCS as they did before. Analysis will be done via analysis of variance (ANOVA), with geographic region, baseline disease severity and treatment as factors in the model. The secondary analysis will apply censoring rule #2 with the same assumptions as described above.

Whether any background TCS is used or not used for each patient is also collected on the diary device in each day starting from the first dose date throughout the study.

The total number of days that the patients did not use background TCS will be summarized by both potencies throughout the entire 16-week treatment period. The main analysis applies censoring rule #1. After patients who are rescued or discontinue IP, it is assumed that background TCS would be applied each day. In case of missing values in the daily diary, it will be assumed that background TCS has been used. Analysis will be done via ANOVA, with geographic region, baseline disease severity and treatment as factors in the model. A secondary analysis will apply censoring rule #2, with the same assumptions for missing values as described above.

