### **6.12.2. Secondary and Exploratory Efficacy Analyses**

For secondary analysis, the null hypotheses is that neither baricitinib 4 mg nor baricitinib 2 mg is superior to placebo in the ITT population. These analyses assume treatment response disappears after patients are rescued or permanently discontinued from treatment and will serve as the primary estimand. In this estimand, missing data due to the application of the primary censoring rule and the occurrence of other non-censor intercurrent events will be imputed using the method described in Table JAIY.6.1.

A supplemental estimand for secondary endpoints is to test the null hypotheses that neither baricitinib 4 mg nor baricitinib 2 mg is superior to placebo in the ITT population. These analyses assume the treatment response disappears after patients permanently discontinued from treatment. In this supplemental estimand, missing data due to the application of the secondary censoring rule and the occurrence of other non-censor intercurrent events will be imputed using the method described in Table JAIY.6.1.

A list of exploratory endpoints are provided in Section 4.2.2. There will be no adjustment for multiple comparisons for exploratory endpoints. The secondary and exploratory efficacy

endpoints are detailed in [Table JAIY.6.4](#) and analyses are provided in [Table JAIY.6.5](#). Health outcomes analyses are described in [Section 6.13](#).

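### After rescue or stopping drug, the two background-TCS endpoints rest on incompatible assumptions, and no planned gram analysis tests loss of benefit after drug is permanently stopped

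*SAP*

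**What the plan says.** SAP 4.2.2 lists two background-TCS endpoints among the other secondary objectives, without multiplicity adjustment: mean grams used over 16 weeks, from tube weights, and mean number of days without TCS over 16 weeks, from the daily diary. SAP 6.11.1 sets out how each is analysed.

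- **Grams.** "The main analysis on the total amount of background TCS throughout the entire 16-week treatment period will apply censoring rule #1". After rescue or stopping investigational product (IP), whichever comes first, "it is assumed that they would use the same amount of TCS as they did before". Then: "The secondary analysis will apply censoring rule #2 with the same assumptions as described above".
- **TCS-free days.** "The main analysis applies censoring rule #1". The assumption made for the same events is different, however: "After patients who are rescued or discontinue IP, it is assumed that background TCS would be applied each day".

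Section 6.11.1 numbers the censoring rules, whereas SAP 6.4 names them. I read #1 as the primary rule, which "will censor efficacy and health outcome data after permanent study drug discontinuation or after rescue therapy", and #2 as the secondary rule, which censors only after permanent drug discontinuation.

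For secondary endpoints in general, SAP 6.12.2 states: "These analyses assume treatment response disappears after patients are rescued or permanently discontinued from treatment and will serve as the primary estimand".

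**The concern.** The same patient, with the same event under the same censoring rule, is given two different futures. A patient using no TCS who then stops drug for an adverse event is counted as using TCS on every remaining day for one endpoint and as using 0 g for the other. The SAP gives no reason for the difference.

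The days rule fits the 6.12.2 assumption that response is lost. The gram rule does not. It carries the patient's pre-event level forward, and SAP 6.4.3 itself says of carry-forward that it takes the treatment effect to persist after the event. Elsewhere the SAP uses carry-forward as a sensitivity analysis to the repeated-measures model; for grams it is the main analysis. The rule #2 gram analysis makes the same assumption after permanent discontinuation, so the two gram analyses cannot check each other on this point.

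At stake is what a TCS-sparing claim can support. The gram and day results could disagree because of the fill-in rule alone, and the gram result keeps whatever arm difference existed before the event.

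**Working it through.** The documents give no planning figure, use rate or event rate for either TCS endpoint, so there is no stated figure to reproduce. The grams per day, event shares and event days below are assumptions. The 112-day treatment period is from the protocol's Schedule of Activities.

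**1. One patient, both rules.** Let g be grams per use-day, s the share of pre-event days with TCS use, and d the event day. Read the carried amount as the mean daily rate.

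- Grams under the gram rule: 112 × s × g.
- Grams if the days rule also governed grams: d × s × g + (112 − d) × g.
- TCS-free days under the days rule: d × (1 − s).
- TCS-free days if pre-event use were carried forward: 112 × (1 − s).

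With g = 2 and d = 28:

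| s | Grams, gram rule | Grams, daily use after event | TCS-free days, days rule | TCS-free days, carried forward |
|---|---|---|---|---|
| 0 | 0 | 0 + 168 = 168 | 28 | 112 |
| 0.3 | 67.2 | 16.8 + 168 = 184.8 | 19.6 | 78.4 |
| 0.5 | 112 | 56 × 0.5 + 168 = 196 | 14 | 56 |
| 1.0 | 224 | 56 + 168 = 224 | 0 | 0 |

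The rules agree only at s = 1. For any smaller share both can hold only if grams per use-day fall after the event.

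**2. One arm against placebo.** Assume 1.6 g/day on placebo and 1.0 g/day on drug, and that patients with events use TCS like the rest of their arm beforehand.

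- Gram rule: 112 × (1.6 − 1.0) = 67.2 g, whatever the event rate.
- If a fraction f of the drug arm moves to the placebo rate after Day d: 67.2 − f × (112 − d) × 0.6.

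| Event day | f = 10% | f = 30% |
|---|---|---|
| 28 | 67.2 − 5.0 = 62.2 g | 67.2 − 15.1 = 52.1 g |
| 56 | 67.2 − 3.4 = 63.8 g | 67.2 − 10.1 = 57.1 g |

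The reductions are 7.5% and 22.5% for Day 28, and 5% and 15% for Day 56.

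**3. The carried amount is not defined.** SAP 6.11.1 uses intervals of 1, 1, 2, 4, 4 and 4 weeks. Protocol 7.7.2 has moderate-potency TCS at least daily until control, then a step-down and stop, so early use is plausibly heavier. Assume 20 g in Week 1, 10 g in Week 2, 5 g/week in Weeks 3 and 4, and a stop at Week 4, leaving 12 weeks.

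- Last-interval rate: 12 × 5 = 60 g filled in.
- Mean rate: (20 + 10 + 5 + 5)/4 = 10 g/week, and 12 × 10 = 120 g filled in.

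The wording permits either, a factor of two.

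**4. Standard error.** Take four equal periods with variance s² (here s is a standard deviation) and common correlation ρ. The true total has variance 4s² + 12ρs² = 4s²(1 + 3ρ). Doubling the first two periods gives 4 × (2s² + 2ρs²) = 8s²(1 + ρ). The second minus the first is 4s²(1 − ρ), which is never negative. Scaling up a patient's own use does not shrink the between-patient variance in this model.

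**The case against.** The strongest defence is that the SAP uses different estimands for different data types. SAP 6.4.1 applies a composite strategy to categorical endpoints. SAP 6.4.2 says the repeated-measures model for continuous endpoints implies a hypothetical strategy, as if patients had stayed on their initial treatment. Grams are continuous, and carrying use forward resembles that strategy. The 6.12.2 sentence covers all secondary analyses yet points to Table JAIY.6.1, which assigns the repeated-measures model to continuous endpoints, so grams are not alone in departing from it. That table also lists placebo-based imputation only for the primary and key secondary endpoints. Moreover, a daily-use rule has no ready gram equivalent, because the documents give no grams per application.

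This weakens the argument from 6.12.2 but does not remove the point. Section 6.11.1 does not invoke a hypothetical strategy, and it applies a different assumption to the companion endpoint without explanation.

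A reader might infer more than the documents support:

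- **That grams are biased in favour of drug.** The direction is not known. Protocol 7.7.4 reserves rescue for patients uncontrolled despite background TCS, who may be heavy users, and front-loaded use can make the carried amount too high.
- **That benefit is always carried past the end of treatment.** This applies only to IP discontinuation and systemic rescue. After topical rescue IP continues (Protocol 7.7.4), and rule #2 then uses observed grams.
- **That the standard error is too small.** SAP 6.4.4 makes a general remark of this kind about carry-forward, but step 4 does not bear it out for this fill-in.

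**Conclusion.** The inconsistency is real and rests on the text alone: the two rules are incompatible for any patient not already using TCS daily, unless the amount per use-day falls. The gram rule does not follow the assumption in 6.12.2. After permanent IP discontinuation both planned gram analyses keep the pre-event arm difference, and nothing tests the alternative.

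The size and direction in the trial cannot be known from the documents. The 5% to 22.5% reductions in the illustration depend on assumed use rates, event shares and event days, and on drug-arm patients moving to placebo-like use. Both endpoints are other secondary and outside multiplicity control, so no primary or key secondary conclusion changes. This is an improvement the sponsor could make to how the TCS-sparing result is supported; the trial's main conclusions do not depend on it.

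**What to change.** Amend SAP 6.11.1 in three places.

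1. State one post-event assumption for both TCS endpoints, in line with 6.12.2. Imputing grams from placebo while leaving the days rule unexplained would still give one patient two futures.
2. Define the carried amount as a rate over a named interval, for example grams per day over the last completed visit interval or over all time before the event.
3. For grams after permanent IP discontinuation, add an analysis that does not carry benefit forward and report it beside the carry-forward result. One option is to impute the remaining interval grams from the placebo arm, adapting SAP 6.4.4 (100 imputations, Rubin's rules), with imputed grams bounded at zero and the unequal interval lengths respected. Another, alone or in addition, is to use observed tube weights where patients stay in the study: Protocol 5.1.2 and 8.1.2 ask them to remain through Week 16, and the Schedule of Activities has returned tubes weighed at each post-baseline visit.

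Topically rescued patients still on IP need not be imputed from placebo, because rule #2 already uses their observed grams.

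The cost is SAP wording and some programming. The stated TCS-sparing effect may come out slightly less favourable.

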6.1. Inclusion Criteria

Informed Consent

- [1] are at least 18 years of age at the time of informed consent.

Note: Use local requirements to provide consent if the age of adulthood is defined as >18 years

- [2] are able to read, understand, and give documented (electronic or paper signature) informed consent.

Type of Patient and Disease Characteristics

- [3] have a diagnosis of AD at least 12 months prior to screening, as defined by the American Academy of Dermatology: Guidelines of care for the management of AD; Section 1. Diagnosis and assessment of atopic dermatitis ([Appendix 7](#)).
- [4] have moderate to severe AD, including all of the following:
 - a. Eczema Area and Severity Index (EASI) score ≥ 16 at screening (Visit 1) and at randomization (Visit 2)
 - b. IGA score of ≥ 3 at screening (Visit 1) and at randomization (Visit 2)
 - c. $\geq 10\%$ of BSA involvement at screening (Visit 1) and at randomization (Visit 2).
- [5] have a documented history by a physician and/or investigator of inadequate response to existing topical medications within 6 months preceding screening as defined by at least 1 of the following:
 - a. inability to achieve good disease control defined as mild disease or better (e.g., IGA ≤ 2) after use of at least a moderate potency TCS for at least 4 weeks, or for the maximum duration recommended by the product prescribing information (e.g., 14 days for super-potent TCS), whichever is shorter. Topical corticosteroids may be used with or without TCNIs.

- b. Patients who failed systemic therapies intended to treat AD within 6 months preceding screening, such as cyclosporine, methotrexate, azathioprine, and mycophenolate mofetil will also be considered as a surrogate for having inadequate response to topical therapy.
- [6] agree to discontinue use of the following excluded medications/treatments for at least 4 weeks prior to randomization (Visit 2) and throughout the study:
- a. oral systemic corticosteroids
 - b. systemic immunomodulators, including, but not limited to, cyclosporine, methotrexate, mycophenolate mofetil, and azathioprine
 - c. any other systemic therapy used to treat AD or symptoms of AD (approved or off-label use)
- [7] agree to discontinue the use of following excluded medications for at least 2 weeks prior to randomization (Visit 2):
- a. TCS or topical immune modulators (e.g., tacrolimus or pimecrolimus)
 - b. Topical phosphodiesterase type 4 (PDE-4) inhibitor (crisaborole)

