7.7.2. Use of Topical Corticosteroids

A washout period of 14 days is required for all TCS prior to randomization at Visit 2.

At baseline (Week 0, Visit 2), patients will receive triamcinolone 0.1% cream (or equivalent-potency TCS) and hydrocortisone 2.5% ointment (or equivalent-potency TCS). See “Choice of Background Topical Corticosteroid” below. Triamcinolone 0.1% cream (moderate-potency TCS) should be applied at least once daily to affected areas until lesions are under control (clear or almost clear). Patients should then switch to hydrocortisone 2.5% ointment (low-potency TCS) and treat previously affected areas once-daily for 7 days and then stop. Hydrocortisone 2.5% ointment (low-potency TCS) may also be used to replace triamcinolone 0.1% cream (moderate-potency TCS) on areas of thin skin (face, neck, folds, and genital areas) and areas with skin atrophy.

If lesions reappear during the course of the study, the patients should resume the once-daily applications of triamcinolone 0.1% cream (moderate-potency TCS) or hydrocortisone 2.5% ointment (low-potency TCS) as described above.

Patients whose lesions persist or worsen despite the use of emollients and low- and/or moderate-potency TCS and/or patients who require daily applications on large surfaces may be considered for topical rescue with high- or ultra-high-potency TCS (Section 7.7.4 for details).

On the days of study visits, topical therapy including TCS should not be applied before the patient has undergone all study procedures and clinical evaluations in order to allow adequate assessment of skin dryness. Inability to follow this guidance for use of TCS will not be considered a protocol violation.

Choice of Background Topical Corticosteroid

Where possible, triamcinolone cream 0.1% and/or hydrocortisone 2.5% ointment will be supplied by the sponsor for use as background TCS. In the event of these specific TCS being unavailable, an alternate, equivalent-potency TCS may be provided by the sponsor (see below). Topical corticosteroid use, when supplied by the sponsor, should be recorded via weight of returned tubes as indicated in the Schedule of Activities (Section 2). In the event that the sponsor is unable to supply TCS, commercially available triamcinolone 0.1% cream and/or hydrocortisone 2.5% ointment may be supplied by the sites.

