9.1.2. Secondary Efficacy Assessments

9.1.2.1. Eczema Area and Severity Index Scores

The EASI assesses extent of disease at 4 body regions and measures 4 clinical signs: (1) erythema, (2) induration/papulation, (3) excoriation, and (4) lichenification each on a scale of 0 to 3. The EASI confers a maximum score of 72. The EASI evaluates 2 dimensions of AD: disease extent and clinical signs (Hanifin et al. 2001).

Body surface area affected by AD will be derived from data collected as part of the EASI assessment.

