### 6.3. Covariate Adjustment

The randomization to treatment groups at Week 0 (Visit 2) is stratified by disease severity (IGA) and geographic region as described in Section 5.1. Unless otherwise specified, the statistical analysis models will adjust for these stratification variables. The covariates used in the logistic model for categorical data will include the parameter value at baseline. The covariates used in the ANCOVA model for continuous data will include the parameter value at baseline. Inclusion of baseline in the model ensures treatment LSM are estimated at the same baseline value. When an MMRM analysis is performed, baseline value and baseline-by-visit interactions will be included as covariates.

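### Adding baseline body surface area to the model for grams of background TCS is a free precision gain of unknown size; the planned ANOVA is valid without it

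*SAP*

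**What the plan says.** SAP 6.11.1 gives the model for total grams over the 16-week period, under censoring rule #1 as the main analysis and rule #2 as the secondary one: "Analysis will be done via analysis of variance (ANOVA), with geographic region, baseline disease severity and treatment as factors in the model". For the number of TCS-free days it gives the same model: "Analysis will be done via ANOVA, with geographic region, baseline disease severity and treatment as factors in the model". BSA appears in neither.

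The general rule is in SAP 6.3: "Unless otherwise specified, the statistical analysis models will adjust for these stratification variables". That section also adds the analysed parameter's own baseline value. TCS use has no on-study baseline, because Protocol 7.7.2 states: "A washout period of 14 days is required for all TCS prior to randomization at Visit 2".

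On how TCS is used, Protocol 7.7.2 says that the moderate-potency cream "should be applied at least once daily to affected areas until lesions are under control". On BSA, Protocol 9.1.2.1 says: "Body surface area affected by AD will be derived from data collected as part of the EASI assessment". The Schedule of Activities places EASI at Visit 2, inclusion criterion 4 sets a 10% BSA floor at that visit, and SAP 6.8.2 lists BSA among the baseline characteristics.

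Both TCS-use endpoints are other secondary objectives without multiplicity adjustment (SAP 4.2.2).

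**The concern.** Most continuous endpoints in this SAP gain precision from their own baseline value. Grams of TCS cannot, because of the washout, so the model is left with two stratification factors and treatment. The severity factor is binary and comes from the IGA, which Protocol 9.1.1 bases on four lesion signs; extent is not among them. Two patients with the same IGA may enter with very different affected areas, from 10% upward. If grams rise with the area treated, that variation stays in the residual and widens the confidence interval for the TCS-sparing effect. A recorded baseline variable that could absorb some of it is left unused.

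**Working it through.** **No plan figure to reproduce.** The documents give no SD, effect size, power or precision figure for either TCS endpoint. The only power statement (Protocol 10.1, SAP 6.1) is for the primary endpoint: 10% versus 30%, 100 per arm, Fisher's exact test, two-sided alpha 0.025. Exact enumeration gives 89.1% against the stated 89%. It has no bearing on TCS use.

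**Inputs.**
- From the documents: 300 patients, 100 per arm, three regions, two severity levels, three arms, two-sided alpha 0.05.
- Assumed: ρ, the partial correlation of baseline BSA with grams given region, severity and treatment. The documents do not supply it, so a range is shown.

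**Formula.** The planned model has 1 + 2 + 1 + 2 = 6 parameters (intercept, region, severity, treatment), leaving 294 residual degrees of freedom; adding BSA leaves 293. Then

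SE ratio (with BSA / planned) = √[(1 − ρ²) × 294/293].

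The equivalent number of patients is 300 / ratio². To express the gain as power, take a true difference for which the planned model has 80% power: (1.960 + 0.842) × √(2/100) = 0.396 residual SD. The 80% is an assumed reference point, not a plan figure.

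| ρ (assumed) | SE ratio | Equivalent n | Power, from 80% |
|---|---|---|---|
| 0 | 1.002 | 299.0 | 79.9% |
| 0.1 | 0.997 | 302.0 | 80.3% |
| 0.2 | 0.982 | 311.4 | 81.5% |
| 0.3 | 0.956 | 328.5 | 83.4% |
| 0.4 | 0.918 | 355.9 | 86.3% |
| 0.5 | 0.868 | 398.6 | 89.8% |

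Break-even is at ρ² = 1/294, so ρ = 0.058. Below that, the lost degree of freedom slightly outweighs the gain; the worst case is a 0.2% larger standard error.

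**Simulation check.** With 3,000 trials per setting, 100 per arm, normal errors and BSA correlated with IGA, the SE ratios at ρ = 0, 0.2, 0.4 and 0.6 were 1.002, 0.981, 0.916 and 0.798. The formula gives 1.002, 0.982, 0.918 and 0.801. The ANOVA without BSA had bias of at most 0.005 SD and type I error of 4.1% to 5.3%.

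**Chance imbalance in one trial.** The standardized BSA difference between two arms of 100 has SD √(2/100) = 0.14. At ρ = 0.4, a 2-SD imbalance (0.28) moves the estimate by 0.4 × 0.28 = 0.11 residual SD, about 0.8 of its standard error (0.11/0.14). The planned standard error already allows for this over repeated trials, so it is the same precision point and not an additional one.

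**The case against.** The strongest reply is that nothing is wrong with the plan. The model follows SAP 6.3, and the Patient Benefit Index, which also has no baseline, gets the same treatment (Table JAIY.6.7, footnote a). That stands: a reader might infer an error, an internal contradiction or a biased estimate, and the documents and the simulation support none of these.

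The second reply is that the correlation is assumed. Grams over 16 weeks also depend on response and duration of use. Other topical agents may replace TCS on problem areas. Only sponsor-provided tubes are totalled, unweighed partly used tubes count as half, and use after rescue or discontinuation is extrapolated. This stands as a reason why ρ may be small. It does not make ρ zero, and the cost if it is zero is negligible.

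A reader might also infer that both TCS endpoints demonstrably lose precision. The documents do not support that. TCS-free days records any use or none, so treating 10% or 60% of BSA once a day scores the same. Missing diary days, and days after rescue or discontinuation, are set to use whatever the BSA. Extent could still act indirectly: large treated surfaces are a ground for considering topical rescue (Protocol 7.7.2 and 7.7.4), and days after rescue count as use under rule #1. That route is weaker, and it falls away under rule #2 if, as I read it, this is the secondary rule of SAP 6.4, which censors only at study drug discontinuation.

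**Conclusion.** The point holds as an efficiency improvement for grams of TCS. Baseline BSA is collected, plausibly related to the amount applied and not scored by the IGA, yet it is left out of the model. The size is unknown: a standard error about 2% smaller at ρ = 0.2, 4% at 0.3, 8% at 0.4 and 13% at 0.5, with nothing gained near zero. These figures rest on the assumed ρ, a linear relation and 100 analysed patients per arm. For TCS-free days a smaller gain is possible, but no figure can be given.

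**What to change.** In SAP 6.11.1, before unblinding, change the grams analysis from ANOVA to ANCOVA by adding baseline BSA as a continuous covariate, with region, baseline disease severity and treatment kept, under both censoring rules. The same covariate may be added to the TCS-free-days model so that the two analyses match. The baseline definition in SAP 6.2.2 already covers BSA.

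The cost is one phrase in the SAP, one term in the program and one degree of freedom, with no new data. Once the data are unblinded, the adjusted model should be reported only as a supplementary post hoc analysis beside the prespecified ANOVA.
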